8. SELECTION OF SUBJECTS

8.1. Subject Inclusion Criteria

To qualify for study participation, the subject must meet all of the following inclusion criteria:

1. Subject is 18 to 65 years of age, inclusive, at the time of informed consent with bipolar I disorder, current episode depressed with or without rapid cycling disease course (≥ 4 episodes of mood disturbance but < 8 episodes in the previous 12 months) with or without psychotic features (diagnosed by DSM-5 criteria, and confirmed by the SCID-5-CT). The current episode of major depression associated with bipolar I disorder must be confirmed by the Investigator and noted in the source records.
2. Subject provides written informed consent and is willing and able to comply with the protocol in the opinion of the investigator.
3. Subject or legally acceptable representative must possess an educational level and degree of understanding of English or the local language that enables them to communicate suitably with the Investigator and the study coordinator.
4. Subject must have a lifetime history of at least one bipolar manic or mixed manic episode. It is strongly recommended that a reliable informant (eg, family member or caregiver) be available to confirm this history.
5. Subject's current major depressive episode is ≥ 4 weeks and less than 12 months in duration at Screening.
6. Subject has a MADRS total score ≥ 22 at both Screening and Baseline.
7. Subject has a YMRS total score ≤ 12 at Screening.
8. Female subjects of childbearing potential must have a negative serum β -hCG test at Screening.
9. Females who participate in this study must be one of the following:
 - Unable to become pregnant (eg, postmenopausal, surgically sterile, etc.)
 - Practicing abstinence or part of an abstinent lifestyle
 - Using and will continue to use a highly effective form of birth control for at least 28 days prior to administration of the first dose of study drug, during the treatment period, and 2 months after completion or premature discontinuation from the study drug. See [Section 10.4](#) for further information on acceptable methods of birth control.
10. Male subjects with partners of child bearing potential must be practicing abstinence, part of an abstinent lifestyle or using protocol-specified methods of birth control. See [Section 10.4](#) for further information on acceptable methods of birth control.
11. Subject is in good physical health on the basis of medical history, physical examination, and laboratory screening.

12. Subjects with type 2 diabetes are eligible for study inclusion only if all of the following conditions are met within 30 days prior to Screening:
 - Subject's random screening glucose is < 200 mg/dL (11.1 mmol/L).
 - Subject's Hemoglobin A1c (HbA1c) ≤ 7.0%.
 - If a subject is currently being treated with oral anti-diabetic medication(s), the dose must have been stable for at least 30 days prior to screening. Such medication may be adjusted or discontinued during the study, as clinically indicated.
 - Subject has not required hospitalization for diabetes or related complications in the past 12 months.
 - Note: Subjects with type 2 diabetes that is newly diagnosed during screening are ineligible for the study.
13. Subject who requires concomitant medication treatment with the following agents may be included if they have been on stable doses for the specified times: 1) oral hypoglycemics must be stabilized for at least 30 days prior to baseline; 2) thyroid hormone replacement must be stable for at least 90 days prior to baseline; 3) anti-hypertensive agents must be stable for at least 30 days prior to baseline. The subject's medical condition should be deemed clinically stable following consultation with the Medical Monitor as needed.

8.2. Subject Exclusion Criteria

The subjects who meet any of the following criteria will be excluded in the study.

1. Subject has a lifelong history or presence of symptoms consistent with a major psychiatric disorder other than bipolar I disorder as defined by DSM-5. Exclusionary disorders include but are not limited to moderate to severe alcohol use disorder (within past 12 months), substance use disorder (other than nicotine or caffeine) within past 12 months, bipolar II disorder, schizoaffective disorder, obsessive compulsive disorder, posttraumatic stress disorder.
2. Subject demonstrates a decrease (improvement) of ≥ 25% in MADRS total score from Screening to Baseline, or subject's MADRS total score is < 22 at Baseline.
3. Subject has received treatment with antidepressants within 3 days of randomization, fluoxetine at any time within 28 days, an MAO inhibitor within 21 days or clozapine within 120 days. All other psychotropic medications with the exceptions of lorazepam, temazepam, eszopiclone, zopiclone, zolpidem and zolpidem CR require 3 days minimum washout (see [Section 10.3.3](#) for lorazepam, eszopiclone, zopiclone, temazepam, zolpidem, and zolpidem CR treatment restrictions). Depot neuroleptics must be discontinued at least one treatment cycle prior to randomization.
4. Subject has suspected/confirmed Borderline Personality Disorder.
5. Subject currently has a clinically significant neurological, metabolic (including type 1 diabetes), hepatic, renal, hematological, pulmonary, cardiovascular, gastrointestinal, and/or urological disorder such as unstable angina, congestive heart failure (uncontrolled), or central nervous system (CNS) infection that would pose a risk

to the subject if they were to participate in the study or that might confound the results of the study. Subjects with a known history of HIV seropositivity will be excluded.

Note: Active medical conditions that are minor or well-controlled are not exclusionary if they do not affect risk to the subject or the study results. In cases in which the impact of the condition upon risk to the subject or study results is unclear, the Medical Monitor should be consulted. Any subject with a known cardiovascular disease or condition (even if under control) must be discussed with the Medical Monitor before being randomized in the study.

6. Subject has evidence of any chronic organic disease of the CNS such as tumors, inflammation, active (or history of) seizure disorder, vascular disorder, Parkinson's disease, Alzheimer's disease or other forms of dementia, myasthenia gravis, or other degenerative processes. In addition, subjects must not have a history of intellectual disability or persistent neurological symptoms attributable to serious head injury. Past history of febrile seizure, is not exclusionary.
7. Subject has a history of malignancy < 5 years prior to signing the informed consent, except for adequately treated basal cell or squamous cell skin cancer or in situ cervical cancer. Subjects with pituitary tumors of any duration are excluded.
8. Subject demonstrates evidence of acute hepatitis, clinically significant chronic hepatitis, or evidence of clinically significant impaired hepatic function through clinical and laboratory evaluation (use screening values for laboratory evaluation). Subject has a history of stomach or intestinal surgery or any other condition that could interfere with absorption, distribution, metabolism, or excretion of medications.
9. Subject has knowledge of any kind of cardiovascular disorder/condition known to increase the possibility of QT prolongation or history of additional risk factors for torsade de pointes (eg, heart failure, hypokalemia, family history of Long QT Syndrome or Brugada Syndrome) or cardiac conduction disorders, or requires treatment with an antiarrhythmic medication.
10. Subject has family history of QTc prolongation or of unexplainable sudden death at < 50 years of age.
11. Abnormal 12-lead ECG at Screening, including:
 - QTcF > 450 ms (male subjects) or > 470 ms (female subjects)
 - QRS > 110 ms
 - PR > 200 ms
 - Second- or third-degree atrioventricular block
 - Any rhythm other than sinus rhythm, which is interpreted by the Investigator to be clinically significant
12. Subject has a history of neuroleptic malignant syndrome (NMS).
13. Subject exhibits evidence of severe tardive dyskinesia, severe dystonia, or any other severe movement disorder. Severity is to be determined by the investigator.

14. Subject has been diagnosed with type 1 diabetes, or insulin-dependent diabetics.
15. Subject who has any abnormal laboratory parameter at screening that indicates a clinically significant medical condition as determined by the investigator.
 - Subjects with fasting blood glucose at screening ≥ 126 mg/dL (7.0 mmol/L) will be excluded from the study.
 - Subjects with fasting blood glucose from 100-125 mg/dL (5.6-6.9 mmol/L) may enter the study based on the approval of the Medical Monitor.
 - Subjects who are found to have been non-fasting at Screening may be allowed if their blood glucose is < 200 mg/dL. Subjects with random (nonfasting) blood glucose at screening ≥ 200 mg/dL (11.1 mmol/L) must be retested in a fasted state.
 - Subjects with $\text{HbA}_{1c} > 7.0\%$ will be excluded.
16. Subject has a prolactin concentration > 100 ng/mL at screening or have a history of pituitary adenoma.
17. Subject has a body mass index (BMI) ≥ 40 or < 18 kg/m² at Screening.
18. Subject has a history of non-response to an adequate (6-week) trial of three or more antidepressants (with or without mood stabilizers) during the current episode.
19. Subject is considered by the Investigator to be at imminent risk of suicide or injury to self, others, or answers “yes” to “Suicidal Ideation” item 4 (active suicidal ideation with some intent to act, without specific plan) or item 5 (active suicidal ideation with specific plan and intent) on the C-SSRS assessment at the Screening visit (in the past month [30 days]) or Baseline.
20. Subject tests positive for drugs of abuse at screening or baseline. In the event a subject tests positive for cannabinoids (tetrahydrocannabinol), the investigator will evaluate the subject’s ability to abstain from cannabis during the study. This information will be discussed with the Medical Monitor for study enrollment consideration.
21. Subject has a history of hypersensitivity to more than two distinct chemical classes of drug (eg, sulfas and penicillins).
22. Subjects have received depot neuroleptics unless the last injection was at least one treatment cycle before randomization.
23. Subject requires treatment with a drug that consistently prolongs the QTc interval (see [Section 23](#), Appendix IV).
24. Subject has received ECT within 90 days prior to randomization or is expected to require ECT during the study course.
25. Subject is currently participating, or has participated in a study with an investigational or marketed compound or device within 6 months prior to signing the informed consent, or has participated in 3 or more studies within 18 months prior to signing the informed consent.

9. STUDY DRUG MATERIALS AND MANAGEMENT

9.1. Description of Study Drug

SEP-4199 will be supplied as matching 100 mg and 200 mg tablets each containing a fixed ratio of 85:15 (R-amisulpride:S-amisulpride). Two 100 mg tablets will be given for the 200 mg dose. Two 200 mg tablets will be given for the 400 mg dose. Two placebo tablets matching SEP-4199 active tablets will be given for the placebo dose.

Table 5: Investigational Product

Attribute	Investigational Product		
Product name	SEP-4199 100 mg	SEP-4199 200 mg	Matching Placebo
Dosage form	Tablets	Tablets	Tablets
Unit dose	Tablet	Tablet	Tablet
Route of administration	Oral	Oral	Oral
Physical description	Pale orange oval film-coated unmarked tablets	Pale orange oval film-coated unmarked tablets	Pale orange oval film-coated unmarked tablets
Excipients	D-Mannitol, pregelatinized starch, croscarmellose sodium, polyvinyl alcohol, magnesium stearate, hydroxypropyl methylcellulose, Macrogol 400, titanium dioxide, talc, iron oxide yellow, iron oxide red, carnauba wax		

9.2. Study Drug Packaging and Labeling

9.2.1. Package Description

Study drug will be provided in one-week blister cards containing 18 oral tablets of SEP-4199 100 mg, 200 mg, or Placebo tablets (7 days + 2 extra days).

9.2.2. Labeling Description

All labeling and packaging for study drug will be based on all applicable regulatory requirements described in either United States (US) Code of Federal Regulations (CFR), CFR21, Part 312.6, Annex 13 of “The Rules Governing Medicinal Products in the European Community, Volume 4 Good Manufacturing Practice for Medicinal Products,” and/or in accordance with any other local applicable regulatory requirements. Label text may include, but are not limited to, the following information:

- Protocol number
- Sponsor’s name and address
- Compound/Code or name of investigational drug (if needed)
- Contents (eg number of tablets, strength)

- Investigational Drug/caution statement or New Drug statement
- Instructions for use and storage
- Blank space for study center number and date opened (if needed)
- Lot number
- Randomization number (if needed)
- Expiration date (if needed)
- Visit number (if needed)
- Unique medication number (if needed)
- Space for subject identifiers (if needed)
- Investigator information (if needed)

9.3. Study Drug Storage

SEP-4199 tablets and placebo tablets are to be stored between 15°C and 25°C (59°F and 77°F); excursions are permitted to 30°C (86°F), and away from light. The study drug storage area will be monitored for temperature. The subject will be instructed to store the medication at room temperature.

9.4. Dispensing of Study Drug

An IXRS will be used to manage subject screening and randomization, drug dispensation and accountability. The IXRS is an integrated web-based subject and drug management system.

Study drug blister cards will be assigned by the IXRS based on the treatment schedule. The IXRS will generate instructions for which study medication unit/number to assign to a subject. Each subject will be dispensed one or two 9-day blister cards per scheduled visit, depending on the timing of the next scheduled visit (see [Table 2](#)).

The first study drug dose will be taken on Day 1. Subjects will be instructed to take their study drug as a single oral dose once a day in the morning at approximately the same time each day. Study visits will begin no later than 6 hours postdose, if possible. Study drug may be taken with or without food. Clinical site staff will interview the subject for self-report of the last 3 doses and record the date and time of each study drug administration in the source (all visits) and CRF (Visits 4 and 6 only).

Study drug should be maintained under the strict control of qualified site staff at all times. Appropriate guidelines should be followed in proper dispensation to the study participant. Proper handling and storage should be followed. IXRS drug dispensing guidelines should be followed for dispensing study drug to the subject, in addition to all accountability records where required. Specific User Manuals will be supplied.

9.5. Study Drug Accountability

The Investigator or designee is responsible for storing the drug in a secure location and for maintaining adequate records of drug disposition that includes the dates, quantity, and use by

subjects. If the study is stopped for any reason or completed, all unused supplies of drug will be returned to the Sponsor, unless other instructions are provided in writing by Sponsor/CRO.

Upon receipt of study drug, the Investigator or designee will inventory the supplies and verify receipt of supplies. The site will perform an acknowledgement of receipt via the IXRS, confirming the date of receipt, inventory and condition of study drug received.

The IXRS will be used for the accountability of the study drug at the clinical site. The Investigator or designee will maintain the inventory for accountability within the IXRS, including study drug dispensation, return and availability of study drug received. The Investigator or designee will collect and document all used and unused study drug from study subjects at appropriate study visits.

The drug will not be dispensed to any person who is not a study subject under this protocol. Study drug will not be dispensed to any subject following the completion of the 6-week treatment period.

9.6. Study Drug Handling and Disposal

A drug inventory record will be supplied from Sponsor/CRO. The Investigator or designee on an ongoing basis must maintain a drug inventory record of supplied, received, dispensed, and returned medication. The Investigator or designee is required to return all unused study drug to the Sponsor or designee as instructed. The Investigator or designee is required to maintain copies of medication shipping receipts, drug accountability records, and records of return or final disposal of the study drug in accordance with local regulatory requirements.

10. TREATMENT OF SUBJECTS

10.1. Study Drug

SEP-4199 100 mg and 200 mg tablets for 200 mg and 400 mg doses will be supplied as described in [Section 9.1](#).

Study drug tablets will be self-administered by the subject once daily as a single oral dose in the morning at approximately the same time, beginning on Day 1 and continuing through Visit 6 (Day 42 ± 2).

10.2. Treatment Compliance

Subjects will self-report the date and time of their last 3 doses prior to each clinic visit. Site staff will record these last 3 dosing times in the CRF for Visits 4 and 6 and returned drug accountability details in IXRS for each dispensed kit upon return by subject.

10.3. Prior and Concomitant Medications and Therapies

The following information on all concomitant medication administered between Visit 1 and Visit 7 or at discontinuation will be recorded on the CRF: Medication name, dose, frequency, route, start date, stop date, and indication.

Information on the format and version of coding dictionary is provided in the Data Management Plan (DMP). All medications will be coded using WHO-DD.

Initiation of new psychotherapeutic interventions (e.g., a new course of psychotherapy) will not be permitted during the study. Subjects who have participated in ongoing psychotherapy treatment for at least 12 weeks prior to screening will be permitted to continue this treatment during the study.

Any medication or non-pharmacological therapy that is taken by or administered to the subject at any point during the course of this study must be recorded in the eCRF. The entry must include the dose, regimen, route, indication, and dates of use.

10.3.1. Prior Medications

Treatment with all prior psychotropic medications (eg, antipsychotic agents, antidepressants, and mood stabilizers) must be discontinued as tolerated and clinically appropriate at least 3 days or 5 half-lives (whichever is longer) prior to randomization. Treatment with sedative hypnotics (for insomnia) is permitted during the screening period, but should be tapered as clinically appropriate to conform with and adequately prepare the subject for the protocol-specified dosing limitations applicable to these agents following randomization (see [Section 10.3.3](#)). Subjects treated with fluoxetine, or olanzapine plus fluoxetine combination must discontinue these medications at least 28 days prior to randomization. Depot neuroleptics must be discontinued at least one treatment cycle prior to randomization. Subjects treated with MAO inhibitors must discontinue these medications at least 21 days prior to randomization. All other psychotropic medication (except as described in this section), including medication and herbal supplements (eg, Gingko Biloba, Kava Kava, St. John's Wort) must be discontinued as tolerated and clinically

appropriate prior to randomization. Subjects should not be taken off their current effective medications for treatment of bipolar depression for purposes of participating in this protocol.

10.3.2. Concomitant Nonpsychotropic Medications

Non-psychotropic medications used to treat mild, chronic medical conditions may be used during screening and after randomization if the dose and regimen have been stable ($\pm 25\%$) for at least 30 days prior to screening. The concomitant medication dose may change as needed after randomization (or be discontinued). Routine vaccines (ie, seasonal influenza, pneumonia, etc.) are allowed based on Investigator judgement. β -adrenergic antagonists used to treat stable hypertension may be continued through the screening/washout phase and post-randomization. In addition, use of non-prescription pain medications (e.g., aspirin, acetaminophen/paracetamol, ibuprofen) is allowed during all phases of the study provided these medications do not have a propensity for psychotropic effects and do not interfere with the evaluation of study medication. Medications for short-term treatment of a medical condition (no more than 10 days) are allowed without consultation with the Medical Monitor provided that the medications do not consistently prolong the QTc interval (see [Section 23](#), Appendix IV).

10.3.3. Concomitant Psychotropic/Antipsychotic Medications

Treatment with benztropine (up to 6 mg/day) will be permitted as needed for movement disorders. In cases where benztropine is not available or a subject has had an inadequate response or intolerance to benztropine treatment, the following medications may be used to treat acute EPS: biperiden (up to 16 mg/day) or trihexyphenidyl (up to 15 mg/day) or diphenhydramine (up to 100 mg/day). Treatment with propranolol (up to 120 mg/day) or amantadine (up to 300 mg/day) will be permitted as needed for akathisia. These allowed medications for the treatment of EPS, akathisia, and dystonia may be given in any formulation (oral, IM, or IV) as deemed appropriate by the investigator. Medications used to treat movement disorders should not be given prophylactically. Medications used for movement disorders should be tapered and discontinued prior to randomization but may be reinstated if symptoms emerge.

In situations where anticholinergic agents or sedative/hypnotic agents (or any agents that may cause sedation) are administered, these should be taken at the same time each day and should not be taken within 8 hours of scheduled assessments. In regions that do not have the specified drugs available, similar drugs at equivalent dosages will be substituted as described in the Study Reference Manual or in consultation with the Medical Monitor.

Concomitant use of sedative hypnotics is permitted during Screening and for Weeks 1-3 (through Visit 5) at the discretion of the Investigator with the following restrictions: Lorazepam is permitted at the discretion of the Investigator up to 2 mg/day for intolerable anxiety/agitation, as clinically indicated. Lorazepam should be used sparingly, when clinically required, per investigator judgment. Lorazepam (≤ 2 mg/day), eszopiclone (≤ 3 mg/day), zopiclone (≤ 7.5 mg/day), zolpidem (≤ 10 mg/day), zolpidem CR (≤ 12.5 mg/day) and temazepam (≤ 30 mg/day) may be administered at bedtime for insomnia, as needed. Hypnotic agents should be administered no more than once nightly and should not be used in combination. Continued use of the above sedative hypnotics beyond Visit 5 requires approval from the Medical Monitor.

Anxiolytics, sedatives or hypnotics should not be administered within 8 hours prior to any psychiatric assessments.

In regions where lorazepam or zolpidem or other specified medications are not available, another similar agent at equivalent doses will be permitted as specified by the Medical Monitor and/or the Study Reference Manual. Opiates may be allowed in rare cases for a limited period of time with prior authorization from the Medical Monitor.

Subjects who require treatment with one or more of the restricted medications should be excluded or discontinued (as appropriate) from the study. Since the list of medications in [Section 23](#), Appendix IV is not comprehensive, the Investigator should use medical judgment when a subject presents with a medication not on the list or consult with the Medical Monitor for clarification.

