13. MEDICATIONS

Medications will be presented for the SAF population and coded to indication-specific Anatomical Therapeutic Chemical (ATC) Level 3 and PT according to World Health Organization Drug (WHODRUG) drug dictionary, Version 01MAR2017 or higher. If ATC level 3 is missing then ATC level 2 will be used. Medication will be sorted alphabetically by ATC level3 and by decreasing frequency of PT in the All SEP-4199 column.

Whenever available, the time information should be accounted for in the derivation of prior, concomitant, and post-treatment medications, see [APPENDIX 2](#) for the handling of partial dates for medications. In the case where it is not possible to define a medication as prior, concomitant, or post-treatment, the medication will be classified by the worst case; ie, concomitant.

- Prior medications are medications which stopped prior to the first dose of study drug.
- Concomitant medications are medications that:
 - Started prior to, at the time of, or after the first dose of study drug, AND
 - Started before or at the date (day) of the last dose of study drug, AND
 - Ended at the time of or after the first dose of study drug or were ongoing at the end of the study.
- Post-treatment medications are medications which started after the day of the last dose of study drug.

Prior and concomitant medication use will be summarized by treatment group by ATC Level 3 classification and PT using the SAF population. Subjects with multiple uses of a medication will be counted only once for a given drug class or PT. Number and percentage of subjects who take concomitant benzodiazepines, sedatives, or hypnotics will be summarized by visit (including follow-up visit) and overall. Prior, concomitant, and post-treatment medications will be provided in data listings.

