17.6.5. MODIFIED SIMPSON-ANGUS SCALE (SAS)

Document:

Author:

Version Number:

V2.0

Version Date:

21MAY2020

Template No: CS_TP_BS016 Revision 4
Effective Date: 01Apr2016

Reference: CS_WI_BS005

The Modified SAS is a clinician-rated assessment of neuroleptic-induced Parkinsonism consisting of 10 items. Items are anchor-based, rated on a 5-point scale, and address rigidity, gait (bradykinesia), tremor, glabellar tap, and salivation (Simpson 1970). The SAS mean score is defined as the average of all 10 items and ranges between 0 and 4. Lower values of the SAS mean score indicate milder symptoms. If one or more items are missing at a visit the SAS mean score will be set to missing. SAS is assessed at Visit 2/Baseline, Visit 3/Week 1, Visit 4/Week 2, Visit 5/Week 4, and Visit 6/Week 6.

All summaries and analyses will be based on the SAF population. Descriptive statistics for absolute value and change from baseline in SAS mean score will be displayed at each visit by treatment group. The SAS mean score will be analyzed using MMRM and ANCOVA based on the change from baseline to Week 6 similar to the primary efficacy endpoint, with the baseline SAS mean score value as covariate (see [Sections 16.1.3](#) and [16.1.5.1](#)).

The SAS mean score at each visit will also be classified as 'abnormal' if it exceeds 0.3 ([Rush 2000](#)). Otherwise, non-missing mean scores will be classified as 'normal.' Shifts from baseline will be summarized by visit and treatment group.

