0.4 Overall double-blind compliance rate < 75% or > 125%

The overall compliance rate of the double-blind treatment period is calculated as: (number of tablets taken / number of tablets should have been taken) × 100%. Subjects whose overall compliance rate is < 75% or > 125% will be identified programmatically. These subjects will be considered IPDs. Subjects whose overall compliance rate cannot be calculated will not be considered IPDs.

0.5 Received benzodiazepines, sedatives or hypnotics within 8 hours of a subsequent efficacy assessment

Protocol section 10.3.3 specifies: "Benzodiazepines, sedatives or hypnotics should not be administered within 8 hours prior to any psychiatric assessments."

For a given study visit, the date and time of the last dose of benzodiazepines, sedatives or hypnotics taken immediately before the visit, and the collection start date and time of efficacy assessments at the visit, will be used to identify subjects who took any benzodiazepines, sedatives or hypnotics medications within 8 hours of a subsequent efficacy assessment. Such cases will be identified programmatically and flagged in a data listing. The IPD review team will determine whether any of these cases constitutes an IPD.

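### BARS and SAS are analysed with no account of EPS or akathisia rescue, and no planned table gives the number of distinct subjects rescued per arm

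*Protocol*

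**What the plan says.** Protocol 10.3.3 names benztropine for movement disorders. It allows biperiden, trihexyphenidyl or diphenhydramine for acute EPS where benztropine is unavailable, inadequate or not tolerated. For akathisia it adds: "Treatment with propranolol (up to 120 mg/day) or amantadine (up to 300 mg/day) will be permitted as needed for akathisia". Preventive use is barred. Such drugs are to be stopped before randomization and may be restarted if symptoms emerge. Protocol 7.4 lists this allowance as a way to limit dropout.

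SAP 17.6.5 says "The SAS mean score will be analyzed using MMRM and ANCOVA based on the change from baseline to Week 6", and 17.6.4 plans the same for BARS, both in the safety population. Neither section mentions rescue. SAS is also classed normal or abnormal (abnormal if the 10-item mean exceeds 0.3). The BARS global item is classed worsened, unchanged or improved. Both shift tables are by visit.

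SAP 13 plans prior and concomitant medication by arm, ATC level 3 and preferred term. One group gets its own count: "Number and percentage of subjects who take concomitant benzodiazepines, sedatives, or hypnotics will be summarized by visit (including follow-up visit) and overall".

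Protocol 10.3.3 has two 8-hour sentences. The broad one begins "In situations where anticholinergic agents or sedative/hypnotic agents (or any agents that may cause sedation) are administered" and says these "should not be taken within 8 hours of scheduled assessments". The narrow one reads "Anxiolytics, sedatives or hypnotics should not be administered within 8 hours prior to any psychiatric assessments". SAP Appendix 7, item 0.5 is titled "Received benzodiazepines, sedatives or hypnotics within 8 hours of a subsequent efficacy assessment" and gives the protocol's rule as "Benzodiazepines, sedatives or hypnotics should not be administered within 8 hours prior to any psychiatric assessments".

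**The concern.** Rescue here is a post-randomization event driven by the symptom that the scale measures. If SEP-4199 produces akathisia or parkinsonism, more subjects in the active arms will be treated for it, and treated subjects tend to score lower at the next visit. The as-observed difference from placebo is then smaller than it would have been without rescue.

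That direction matters for this product. Protocol 4.3 rests its benefit-risk case on limiting D2-related side effects, so a small difference on BARS or SAS would be read as support.

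A count of subjects who needed rescue would put the scale results in context, because effective rescue does not lower it. The sponsor plans such a count for sedatives but not for EPS or akathisia drugs.

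**Working it through.** **1. What the general medication table can show.** Under SAP 13 each rescue drug has a count by arm. Four things stop that table from giving the number of subjects rescued:
- A subject is counted once per class or preferred term, so someone who took two drugs sits on two rows and the rows cannot be added.
- The recorded indication is collected (Protocol 10.3) but not used as a row or filter. Protocol 10.3.2 allows beta-blockers for stable hypertension, so propranolol for akathisia cannot be reliably told apart. Coding is described as indication-specific at ATC level 3; whether that separates the two uses cannot be settled from the documents.
- Drugs begun before the first dose and continued also count as concomitant.
- There is no count by visit.

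**2. How a case can be missed on the scale.** Ratings fall on Days 7, 14, 28 and 42. A subject who develops symptoms after one visit and is treated before the next may never have a raised score. A worst-value row would not recover the case. The SAS class is also sensitive: a total of 4 gives 4/10 = 0.4 (abnormal) and a total of 3 gives 3/10 = 0.3 (normal), so a one-point fall on one item can reclassify a subject.

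**3. Illustration of attenuation (all inputs assumed; none are in the documents).**

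BARS total: akathisia in 12% of active and 3% of placebo subjects, each adding 4 points. Without rescue the mean difference is (0.12 − 0.03) × 4 = 0.36. If a fraction r of cases is on rescue when rated, and a share k of the score remains, the observed difference is 0.36 × [(1 − r) + r × k]:
- r = 0.3, k = 0.25: 0.36 × 0.775 = 0.279 (22.5% smaller)
- r = 0.6, k = 0.25: 0.36 × 0.55 = 0.198 (45% smaller)
- r = 0.6, k = 0: 0.36 × 0.40 = 0.144 (60% smaller)

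The percentage depends only on r and k, provided these are equal in both arms.

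SAS abnormal class: placebo 5%, and a share m of abnormal subjects rescued and scored normal in both arms. The observed difference is (active − 5%) × (1 − m):
- Active 10%: 5.0 points falls to 3.75 (m = 0.25) or 2.5 (m = 0.5)
- Active 15%: 10.0 falls to 7.5 or 5.0
- Active 20%: 15.0 falls to 11.25 or 7.5

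**4. The 8-hour rule, side by side.**
- Protocol, broad sentence: anticholinergics, sedative/hypnotics and any sedating agent; scheduled assessments.
- Protocol, narrow sentence: anxiolytics, sedatives, hypnotics; psychiatric assessments.
- SAP item 0.5: benzodiazepines, sedatives, hypnotics; efficacy assessments only.

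The SAP therefore changes one word of the narrow sentence (Benzodiazepines for Anxiolytics), narrows the assessments, and does not implement the broad sentence. An important protocol deviation (IPD) decides per-protocol membership (SAP 5.2), while BARS and SAS are analysed in the safety population. Widening item 0.5 would not change a single movement-scale result.

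**5. Are dose times available?** Protocol 10.3 lists name, dose, frequency, route, start and stop dates, and indication. SAP 6.3, Table 1 has a last-dose item for benzodiazepines, sedatives and hypnotics only. A timed 8-hour check on anticholinergics cannot be assumed feasible.

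**The case against.** A reader might infer that EPS rescue is counted nowhere. The documents do not support that: SAP 13 and Protocol 15.3.6.9 give each drug by arm. Nor is rescue the only measure that treatment leaves intact. A symptom that emerges after dosing is an adverse event (Protocol 12.1.1), and SAP 17.1.1 tabulates these by arm, including by high level term. Treated akathisia should appear there. This stands, and it limits the harm. Adverse event tables do not adjust the scale analyses, however, and SAP 17.1 specifies no EPS grouping.

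A reader might also infer that the gap in item 0.5 lets drug-lowered scores through. It does not, because IPDs act on the per-protocol population only. Limiting the check to efficacy assessments also fits that population's purpose. Manual review of medication listings (item 0.2) and of the deviations log could still catch a case.

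Analysing safety scales as observed is an ordinary choice, and no safety objective asks for the effect without rescue. This stands, so the request is for an added sensitivity analysis, not a replacement.

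Finally, the illustration rests wholly on assumed inputs. This stands too: it shows a mechanism, not this trial's risk.

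**Conclusion.** A cheap improvement, not a flaw that undermines the safety analysis. BARS and SAS are analysed without regard to symptom-driven rescue, and no planned table gives distinct subjects rescued, by indication or by visit. Any bias toward no difference is conditional: the drug must cause these symptoms, rescue must be used, and it must lower the scores. Its size is unknown.

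Two further readings go too far. Lowered BARS ratings cannot be said to pass as normal, because BARS has no such class; they could count as unchanged. Nor is there a basis for extending the point to AIMS, since nothing in the documents says that the permitted drugs lower AIMS scores.

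The misquotation and incomplete check in item 0.5 are real but separate, with consequences for per-protocol membership only.

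**What to change.** 1. In SAP 13, add the number and percentage of subjects per arm, overall and by visit, who start any drug named in Protocol 10.3.3 for EPS, akathisia or dystonia after the first dose, selected by drug and recorded indication.

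2. In SAP 17.6.4 and 17.6.5, add a sensitivity version of the shift tables. Count a subject as worsened on BARS from the first rescue for akathisia, and as abnormal on SAS from the first rescue for parkinsonism or EPS. Do not apply one rescue to all scales, and leave AIMS as observed.

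3. In Appendix 7, item 0.5, correct the quotation and cite both 8-hour sentences. List use of anticholinergic or other sedating drugs that overlaps an efficacy visit for manual IPD review.

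4. Reconcile Protocol 10.3.3 with 10.3.4 before item 0.2 is applied. The first permits propranolol and amantadine for akathisia; the second leaves both out of its exceptions to the ban on movement-disorder drugs.

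The cost is one table, one sensitivity run and some SAP wording, from drug, date and indication fields already collected. The 8-hour check will remain incomplete, because dose times for these drugs are not listed as collected.
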